#### 7.7.1 Respiratory Tract Specimens

For patients with HABP, VABP, or VP, the BPP rapid diagnostic testing at Screening should be conducted using BAL-like specimens (BAL or mini-BAL) or endotracheal aspirate by Protected Endotracheal Catheter specimens, as applicable. See the Laboratory Manual for further details.

For patients with HABP, VABP, or VP that were diagnosed with a positive BPP rapid test of their respiratory specimen at Screening, respiratory specimens for culture and susceptibility testing must be collected again at Screening. All HABP/VABP/VP patients should have additional specimens collected on Day 5, Day 7, EOT, TOC, LFU, and ET Visits from the respective sites as clinically indicated.

Acceptable specimens for culture and susceptibility testing should include at least 1 positive pretreatment sample (ie, sample obtained prior to study drug dosing) obtained by Protected Specimen Brush with BAL or mini-BAL, by non-bronchoscopic BAL, by Protected Endotracheal Catheter suction, or from culture of lung tissue or pleural fluid obtained prior to randomization and treatment. Non-ventilated patients may have specimens obtained via deep expectoration or expectorated/induced sputum or culture of pleural fluid or lung tissue.

All respiratory specimens, even if positive by BPP rapid test for ABC, should be sent to the local microbiology laboratory for Gram stain (expectorated sputum only), culture and pathogen identification, susceptibility testing, and quantification (BAL only).

To be adequate, respiratory samples from expectorated or induced sputum should show <10 squamous epithelial cells and >25 polymorphonuclear neutrophils per 100 × field. Specimens should be cultured regardless of determination of adequacy. However, if the specimen is deemed to be inadequate, another respiratory sample should be collected and cultured.

Gram stains will be conducted per institutional standards, and Gram stain data should be captured in source documents. Colony counts are not expected to be performed on expectorated or induced

sputum or endotracheal aspirate. If the sputum is cultured, isolates of all pathogens exhibiting significant growth identified by the site laboratory's routine procedures should be sent to the central laboratory, even if the organisms are from a specimen that does not meet the specimen adequacy criteria described above. Culture-purified isolates of pathogens from respiratory samples will be sent to the central laboratory for confirmation of identification and susceptibility testing.

### 7.7.2 Blood Specimens

Two sets of samples from 2 separate venipuncture sites are required for blood cultures in all patients. Each set of blood culture samples will be collected from a separate venipuncture site and will consist of 1 aerobic and 1 anaerobic blood culture bottle (an additional aerobic bottle is allowed if an anaerobic culture is not standard practice at the site). Each set of blood cultures should be collected by direct venipuncture from independent sites approximately 15 minutes to 30 minutes apart. A positive blood culture for ABC within 72 hours prior to randomization can be used for enrollment of a patient as long as the sample was drawn from a peripheral vein or through a newly inserted catheter; however, 2 sets of blood cultures, as outlined above, must be repeated within 24 hours prior to randomization. For a patient to meet criteria for catheter-related bloodstream infection, please see the necessary sampling procedures described in Part A-Specific Inclusion Criterion 1 ([Section 4.1.2](#)). If Screening/baseline blood cultures are positive for ABC, repeat blood cultures should be obtained daily until negative or the patient is a treatment failure. To avoid unnecessary blood draws, the Investigator may wait until the result of the prior blood culture is known before performing the next blood culture.

Additional blood cultures, including blood cultures taken during fever spikes (oral or tympanic temperature  $\geq 38^{\circ}\text{C}$  [ $\geq 100.4^{\circ}\text{F}$ ] or rectal/core temperature  $\geq 38.3^{\circ}\text{C}$  [ $\geq 100.9^{\circ}\text{F}$ ]), may also be collected at the Investigator's discretion.

Isolates of pathogens (eg, not considered to be a contaminant as outlined in the Microbiology Laboratory Manual) from each individual positive blood culture will be sent to the central laboratory.

### 7.7.3 Urine Specimens

For patients with cUTI or AP, urine samples will be collected at Screening, Day 5, Day 7, EOT, TOC, LFU, and ET Visits by 1 of the following methods that minimizes the risk of bacterial contamination:

- Clean-catch mid-stream;
- Newly inserted Foley catheter (bag specimens are not permitted);
- Bladder needle aspiration;
- Suprapubic catheter;
- Ureter aspiration; or
- Nephrostomy tube.

Urine cultures will be performed by the local laboratory. The local laboratory will culture each sample for species identification, quantification, and susceptibility testing. Any organism isolated from the urine will be identified by genus and species by the local laboratory. Culture-purified isolates of potential pathogens isolated at baseline and all post-baseline organisms culture-purified

at the local laboratory and not considered to be contaminants as outlined in the Microbiology Laboratory Manual will be sent to the central laboratory for confirmation of identification and susceptibility results. A urine sample taken to support diagnosis or to treat a medical condition within 48 hours prior to the first dose of study drug can be used for baseline microbiologic assessments if the organism(s) cultured was obtained and stored for shipment to the designated central laboratory. Otherwise, a repeat urine sample for baseline microbiologic assessments is required.

Baseline urine cultures must grow 1 or 2 defined bacterial pathogens, each at  $\geq 10^5$  colony-forming units (CFU)/mL. If a patient grows  $\geq 3$  organisms in the urine, the urine culture will be considered contaminated unless  $\geq 1$  of the organisms also grows in a concurrently obtained blood culture.

For post-baseline urine cultures, only those potential pathogens that grow at  $\geq 10^3$  CFU/mL and deemed not to be contaminants as outlined in the Microbiology Laboratory Manual will be culture-purified and sent to the central laboratory for confirmation of identification and susceptibility testing.

#### 7.7.4 Surgical or Post-Traumatic Wound Specimens

For patients with surgical or post-traumatic wound infections, an adequate clinical specimen for microbiologic evaluation will be collected at Screening, Day 5, Day 7, EOT, TOC, LFU, and ET Visits as long as clinically indicated (ie, as long as there is material to send for culture). Clinical specimens include pus from a wound or abscess and aspirate from the leading edge of cellulitis.

All specimens should be sent to the local laboratory for Gram stain, species identification, and susceptibility testing.

Isolates of potential pathogen(s) culture-purified at the local laboratory will be sent to the central laboratory for confirmation of identification and susceptibility testing results.

### 7.8 Microbiologic Outcome

#### 7.8.1 Microbiologic Outcome for Bacteremia, Complicated Urinary Tract Infection, or Acute Pyelonephritis

For patients with bacteremia, cUTI, or AP, per-patient microbiological response will be determined programmatically as 1 of the following outcomes based on the results of blood and/or urine cultures at the Day 5, Day 7, EOT, TOC, and LFU Visits. A microbiological favorable assessment will include eradication and presumed eradications, as detailed below.

##### Microbiologic eradication:

- For patients with cUTI or AP: the baseline strain of ABC is reduced to  $< 10^3$  CFU/mL on urine culture and negative on repeat blood culture (if positive at baseline); or
- For patients with bacteremia: absence of the baseline strain of ABC on culture.

Microbiologic presumed eradication: no culture was done, and the patient meets clinical criteria for clinical cure.

Microbiologic persistence:

- For patients with cUTI or AP: the demonstration that the urine culture grew  $\geq 10^3$  CFU/mL of the baseline strain of ABC identified at study entry and/or a blood culture demonstrates the same baseline pathogen(s); or
- For patients with bacteremia: presence of the baseline strain of ABC on repeat culture.

Patients who are a persistence at EOT will be considered a persistence at TOC.

Microbiologic presumed persistence: no culture was done, and the patient meets clinical criteria for clinical failure.

Microbiologic indeterminate: if clinically indicated (for cUTI and bacteremia only), no follow-up culture is available, the culture cannot be interpreted for any reason, or the culture is considered contaminated.

Microbiologic recurrence:

- For patients with cUTI or AP: the demonstration that the urine culture grew  $\geq 10^3$  CFU/mL of the baseline strain of ABC identified at study entry at any time after documented eradication at the TOC Visit up to and including the LFU Visit; or
- For patients with bacteremia: a positive blood culture for ABC at any time after documented eradication at the TOC Visit up to and including the LFU Visit.

7.8.2 Microbiologic Outcome for Hospital-Acquired Bacterial Pneumonia, Ventilator-Associated Bacterial Pneumonia, Ventilated Pneumonia, or Surgical or Post-Traumatic Wound Infections

Microbiologic presumed eradication: no culture was done, and the patient meets clinical criteria for clinical cure. For patients with HABP/VABP/VP or surgical or post-traumatic wound infections, where repeat culture samples may not be indicated, presumed eradication based on clinical improvement will be inferred.

Microbiologic presumed persistence: no culture was done, and the patient meets clinical criteria for clinical failure.

## 7.9 Pharmacokinetic Assessments

### 7.9.1 Intense Pharmacokinetic Sampling

The first approximately 30 patients randomized in Part A will have samples collected for intense PK analysis to ensure that exposures observed in this severely ill cohort are comparable to those observed thus far in prior clinical studies. Intense PK sampling will also be performed on the first approximately 20 patients randomized in Part A at sites in China Mainland.

Samples for intense PK analysis will be collected on Day 1, preferably after the second infusion, as follows:

- At the end of the infusion after the infusion pump is turned off (+15 minutes);
- 1.5 hours ( $\pm 15$  minutes) after the end of infusion; and
- Immediately prior to the start of the next infusion.

When possible, PK samples should be collected after the second infusion on Day 1. If the second infusion happens during the night and it is not possible to collect the PK sample after the infusion, the same procedures could be done after the third infusion on Day 1. The PK sample should be taken after the patient received at least 2 infusions on Day 1.

Additional samples for intense PK analysis will be collected on Day 4 ( $\pm 1$  day) as follows:

- At the end of any infusion after the infusion pump is turned off (+15 minutes); and
- Immediately prior to the start of the next infusion.

Table 4 shows the sampling times for intense PK assessments.

**Table 4. Sampling Times for Intense Pharmacokinetic Assessments**

PK Sampling Time	Day 1 [1]	Day 4 ( $\pm 1$ Day)
End of infusion (+15 minutes) [2]	X	X
1.5 hours ( $\pm 15$ minutes) after end of infusion	X	
Immediately prior to the start of the next infusion	X	X
1. PK sample should be taken preferably after the second infusion on Day 1. 2. PK sample should be taken at the end of the infusion after the infusion pump is turned off. PK = pharmacokinetic.		

### 7.9.2 Sparse Pharmacokinetic Sampling

All other patients enrolled in the study (Parts A and B) will have samples collected for sparse PK analysis. Samples for sparse PK analysis will be collected on Day 1, preferably after the second infusion, and on Day 4 as follows:

- On Day 1, immediately prior to the start of the next infusion; and
- On Day 4 ( $\pm 1$  day), immediately prior to the start of the next infusion.

When possible, PK samples should be collected after the second infusion on Day 1. If the second infusion happens during the night and it is not possible to collect the PK sample after the infusion, the same procedures could be done after the third infusion on Day 1. The PK sample should be taken after the patient received at least 2 infusions on Day 1. Table 5 shows the sampling times for sparse PK assessments.

**Table 5. Sampling Times for Sparse Pharmacokinetic Assessments**

PK Sampling Time	Day 1 [1]	Day 4 ( $\pm 1$ Day)
Immediately prior to the start of the next infusion	X	X
1. PK sample should be taken preferably after the second infusion on Day 1. PK = pharmacokinetic.		

The PK samples will be collected for both treatment groups in Part A to keep the study data blinded. The PK samples obtained from the ETX2514SUL group will be analyzed for ETX2514 and sulbactam concentrations using a validated assay by a central bioanalytical laboratory.

The PK plasma samples will be used to estimate PK parameters using non-compartmental methods, such as area under the concentration-time curve, maximum plasma concentration, time to maximum plasma concentration, drug clearance, half-life, minimum plasma concentration, and

steady-state volume of distribution for ETX2514SUL. Population PK and PK/PD modeling will be performed and reported separately. The results will not be included in the clinical study report.

Additional PK sampling may be performed as needed for patients with eGFR >130 mL/min/m^2 undergoing acute hemodialysis or renal replacement therapy utilizing the trough sampling approach.

The actual PK sampling times will be captured on the eCRF. Actual dosing time will also be captured on the eCRF. Actual sampling time will be used for the PK calculations.

See the Laboratory Manual for more details about PK sampling.

## **8 SAFETY ASSESSMENTS**

### **8.1 Adverse Events**

An adverse event is defined as any untoward medical occurrence in a clinical investigation patient administered a pharmaceutical product, which does not necessarily have a causal relationship with this treatment. An adverse event can therefore be any unfavorable and/or unintended sign (including an abnormal laboratory finding), symptom, or disease temporally associated with the use of an investigational medicinal product, whether or not related to the investigational medicinal product. All adverse events, including observed or volunteered problems, complaints, or symptoms, are to be recorded on the appropriate eCRF.

Adverse events, which include clinical laboratory test variables, will be monitored and documented from the time of the main informed consent (not the limited scope ICF) until study participation is complete. This is to be understood that Investigators should report any adverse event occurring from the time the main ICF (including all study procedures) was signed. Investigators are not required to report adverse events occurring for patients who only signed the limited scope ICF (which only allows rapid testing on a respiratory sample). Patients should be instructed to report any adverse event that they experience to the Investigator. Beginning at enrollment, Investigators should make an assessment for adverse events at each visit and record the event on the appropriate adverse event eCRF.

Wherever possible, a specific disease or syndrome rather than individual associated signs and symptoms should be identified by the Investigator and recorded on the eCRF. However, if an observed or reported sign or symptom is not considered a component of a specific disease or syndrome by the Investigator, it should be recorded as a separate adverse event on the eCRF. Additionally, the condition that led to a medical or surgical procedure (eg, surgery, endoscopy, tooth extraction, or transfusion) should be recorded as an adverse event, not the procedure.

Any medical condition already present at Screening should not be reported as an adverse event unless the medical condition or signs or symptoms present at baseline changes in severity or seriousness at any time during the study. In this case, it should be reported as an adverse event.

Clinically significant abnormal laboratory or other examination (eg, ECG) findings that are detected during the study or are present at Screening and significantly worsen during the study should be reported as adverse events. The Investigator will exercise his or her medical and scientific judgment in deciding whether an abnormal laboratory finding or other abnormal assessment is clinically significant. Clinically significant abnormal laboratory values occurring during the clinical study will be followed until repeat tests return to normal, stabilize, or are no longer clinically significant. Any abnormal test that is determined to be an error does not require reporting as an adverse event.

Newly emergent infections that appear after baseline will be reported as adverse events and summarized separately. Clinical failures should not be considered adverse events and should not be reported as such.

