#### **1.4 Risk/Benefit**

No unique contraindications have been determined for ETX2514. Contraindications to the use of sulbactam include a history of hypersensitivity or allergic reactions to sulbactam or any cephalosporin, penicillin, or carbapenem.

ETX2514 was well tolerated in repeat dose animal toxicology studies; no specific safety signals were observed that require special monitoring in human subjects. Reductions in absolute neutrophil count and monocytes were reported in the dog repeat dose toxicity studies and will be monitored by routine hematology assessments in human subjects.

Studies in healthy adult and elderly subjects and in patients with renal impairment or cUTI have revealed no serious adverse drug reactions or deaths to date, and the withdrawal rate due to adverse events has been low (1%). Adverse events have generally been mild to moderate in severity. The most common treatment-emergent adverse events (TEAEs) in both healthy elderly subjects and in patients have included injection site reactions/pain and headache; the less common TEAEs in patients were nausea, diarrhea, and vomiting. Overall, ETX2514SUL has been well tolerated, and only 1 drug-unrelated serious adverse event (SAE) has been reported to date. Doses of ETX2514SUL must be adjusted in patients with impaired renal function. Mild decreases from baseline in mean WBC and neutrophil counts have been observed in subjects receiving ETX2514 alone or multiple doses of ETX2514 with imipenem/cilastatin. Mild increases in alanine aminotransferase (ALT) were observed with administration of ETX2514SUL with imipenem/cilastatin. These findings were not considered clinically significant since mean values remained within the reference range at all time points. However, WBC counts and hepatic function will be monitored closely in ongoing clinical studies. No clinically significant changes in vital signs or ECG parameters have been observed in patients treated with ETX2514SUL with or without imipenem/cilastatin.

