## **7.5 Assessment of Clinical Signs and Symptoms**

Clinical signs and symptoms of the presenting indication will be assessed at Screening, daily during IV treatment beginning on Day 1, at the EOT Visit, at the TOC Visit, at the LFU Visit, and at the ET Visit, if applicable, by the blinded assessor and the unblinded Investigator for Part A and by the unblinded Investigator for Part B. When possible, the same study personnel should complete the assessments at approximately the same time each day. Maximum daily temperature (defined as the maximum temperature reported on a single treatment day) will be recorded. Body temperature may be taken per the site's preferred method, as specified in [Table 3](#), and will be recorded in the appropriate eCRF. The same method of measuring a patient's body temperature should be used throughout the study.

Each sign and/or symptom of the presenting indication will be assigned a classification of absent, mild, moderate, or severe. Findings from the assessment of signs and symptoms will be captured on the appropriate eCRF and should not be documented as adverse events. The signs and symptoms by indication are presented in [Table 3](#).

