## 7.6 Clinical Outcome

Clinical outcome will be used to determine a response of clinical success for all patients. Based on the assessment of signs and symptoms, the unblinded Investigator will choose 1 of the following clinical outcomes at the Day 5, Day 7, EOT Visit, TOC Visit, LFU Visit, and ET Visit, if applicable. In Part A, in addition to the unblinded Investigator, a blinded assessor will also determine clinical outcome. If there is a discrepancy between the assessment of the blinded assessor and unblinded Investigator, the assessment from the blinded assessor will be used. If there is a missing assessment from either the blinded assessor or unblinded Investigator, the other available assessment will be used (see [Section 5.4.1](#)). An adjudication committee may be organized for endpoint adjudication should it be deemed necessary by the DSMB. In such a case, a charter will be developed that describes their activities.

Clinical cure: complete resolution or significant improvement of signs and symptoms that were present at baseline and no new symptoms, such that no additional Gram negative antimicrobial therapy is warranted.

Clinical failure: symptoms present at study entry have not significantly improved or completely resolved, or new symptoms have developed and require the initiation of a non-study Gram negative antibacterial drug therapy, death, or intolerance to study drug leading to discontinuation from the study treatment.

Clinical indeterminate: determination cannot be made because of missing data or the patient is lost to follow-up.

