## 8.2 Serious Adverse Events

An adverse event or adverse reaction is considered serious if, in the view of either the Investigator or Sponsor, it results in any of the following outcomes:

- Death;
- A life-threatening adverse event;

Note: An adverse event or adverse reaction is considered “life-threatening” if, in view of either the Investigator or Sponsor, its occurrence places the patient at immediate risk of death. It does not include an event that, had it occurred in a more severe form, might have caused death.

- Requires hospitalization or prolongation of existing hospitalizations;

Note: Any hospital admission with at least 1 overnight stay will be considered an inpatient hospitalization. An emergency room visit without hospital admission will not be recorded as an SAE under this criterion, nor will hospitalization for a procedure scheduled or planned before signing of informed consent. However, unexpected complications and/or prolongation of hospitalization that occur during elective surgery should be recorded as adverse events and assessed for seriousness. Admission to the hospital for social or situational reasons (ie, no place to stay, live too far away to come for hospital visits) will not be considered inpatient hospitalizations. Adverse events recorded for a patient who is hospitalized for treatment of the underlying illness, do not necessarily meet serious criterion of hospitalization.

- A persistent or significant disability/incapacity or substantial disruption of the ability to conduct normal life functions;
- A congenital anomaly/birth defect; or
- An important medical event.

Note: Important medical events that may not result in death, be life-threatening, or require hospitalization may be considered an SAE when, based upon appropriate medical judgment, they may jeopardize the patient and may require medical or surgical intervention to prevent 1 of the outcomes listed above. Examples of such medical events include allergic bronchospasm requiring intensive treatment in an emergency room or at home, blood dyscrasias or convulsions that do not result in inpatient hospitalizations, or the development of drug dependency.

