#### 9.4.1. Adverse Events

A treatment-emergent adverse event (TEAE) is defined as an adverse event occurring on or after the administration of the first dose of study drug. An overview of adverse events will be provided which summarizes the incidence of the following categories:

- All AEs,
- All TEAEs,
- Drug-related TEAEs,
- TEAEs by severity,
- SAEs,
- Drug-related SAEs,
- SAE leading to death,
- TEAE leading to discontinuation of study drug, and
- SAE leading to discontinuation of study drug.

Patients with multiple events will be counted only once within each category. Severity grade and relationship will be counted using the maximum severity and the strongest relationship respectively for a patient with multiple TEAEs.

The number and percentage of patients reporting a TEAE in each treatment group will be tabulated by SOC and PT; by SOC, PT, and severity; and by SOC, PT, and relationship (related or unrelated to study drug and imipenem/cilastatin). Summary tables will be presented alphabetically by SOC and decreasing frequency of PT in the EXT2514SUL group within SOC. For all analyses of TEAEs, if the same AE (based on PT) is reported for the same patient more than once, the AE is counted only once for that PT and at the highest severity and strongest relationship to study drug.

The number and percentage of patients reporting a drug-related TEAE, a SAE, a treatment emergent SAE, a drug-related treatment-emergent serious adverse event (TESAE), and a TEAE leading to discontinuation of study drug in each treatment group will be summarized by SOC and PT.

A list of patients who have SAEs, a list of patients who discontinue from study drug, and a list of death will be provided. All adverse events will be listed.

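### Protocol 8.1 bars reporting clinical failures as adverse events, but clinical failure is defined to include death and intolerance that stops study drug, so sites hold conflicting AE/SAE instructions

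*Protocol*

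**What the plan says.** The rule is the last sentence of Protocol 8.1: "Clinical failures should not be considered adverse events and should not be reported as such". It follows an instruction to report newly emergent infections as adverse events.

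Protocol 7.6 defines clinical failure, and SAP 5.5.1 repeats the definition. Besides non-improvement and new symptoms that need other Gram-negative treatment, it includes "death, or intolerance to study drug leading to discontinuation from the study treatment".

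Protocol 8.2 defines seriousness this way: "An adverse event or adverse reaction is considered serious if, in the view of either the Investigator or Sponsor, it results in any of the" listed outcomes, of which death is the first. Section 8.3 requires SAE reports within 24 hours and glosses an SAE as an adverse event meeting one of those criteria. Section 8.5 describes how death cases are processed, including possible handling as suspected unexpected serious adverse reactions. Section 9.3 has the DSMB review SAEs and deaths. Protocol 9.2.4 plans a table of patients who stop study drug because of a TEAE. SAP 9.4.1 lists the category "TEAE leading to discontinuation of study drug" and a category for SAEs leading to death.

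A related exemption stands in Protocol 7.5 for signs and symptoms of the presenting indication: "Findings from the assessment of signs and symptoms will be captured on the appropriate eCRF and should not be documented as adverse events". Protocol 8.1 does not count a condition already there at Screening, "unless the medical condition or signs or symptoms present at baseline changes in severity or seriousness at any time during the study"; such a change is reported.

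**The concern.** A site that applies the 8.1 sentence with the only definition of clinical failure in the protocol would not file an adverse event for a patient who dies, or for one stopped for intolerance, once that patient is rated a failure. Because 8.2 and 8.3 build SAEs on adverse events, the exemption would carry through to 24-hour reporting.

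Comparing the safety of the two drugs is a stated secondary objective, and about 100 sites are planned. If sites resolve the conflict differently, the counts of SAEs, drug-related events and TEAEs leading to discontinuation depend partly on which section each site followed. The site investigator is unblinded (Protocol 5.4), so uneven filing could differ by arm, though nothing in the documents shows that it would.

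**Working it through.** The plan states no figure for this point, so there is none to reproduce. The check is a comparison of texts, with one calculation for scale.

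1. **Does 8.1 contain an exception?** No. It uses the term clinical failure without limit.

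2. **Is there another definition that would rescue it?** No. Protocol 7.6 and SAP 5.5.1 give the same definition, and both name death and intolerance that stops treatment.

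3. **Does the exemption reach SAEs?** Read literally, yes. Section 8.3 ties the 24-hour duty to adverse events that meet a seriousness criterion. An event that is not an adverse event does not meet that description.

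4. **What points the other way?**
   - Protocol 8.1 opens with a broad definition covering any untoward occurrence.
   - Section 8.1.1 makes harmful unintended responses to a drug adverse drug reactions, which describes intolerance.
   - Section 8.2 makes death a seriousness outcome.
   - Section 8.5 routes death cases through safety processing.
   - Protocol 9.2.4 and SAP 9.4.1 plan tables that would be incomplete if these events were not filed.

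   Of these, 8.1, 8.1.1, 8.2 and 8.3 address the person filing the report. The others show what the sponsor expects to receive.

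5. **What is captured by other routes?** Day 28 survival is sought for all randomized patients who have not withdrawn consent (7.4). RIFLE nephrotoxicity is graded from creatinine or GFR. The DSMB reviews deaths. Reasons for stopping study drug go into the eCRF (4.3). None of these by itself supplies a causality-assessed, coded event reported within 24 hours.

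6. **Scale.** The inputs are the mortality rates in Protocol 9.2.5 (36% and 41%) and 120 patients, taken as 60 per arm. Expected deaths are 60 × 0.36 + 60 × 0.41 = 21.6 + 24.6 = 46.2, or 46.2 / 120 = 38.5%. This is every assumed death. Not all would be rated clinical failures. On a 7-day course EOT falls on Day 7 or 8, and LFU is 14 ± 2 days later, between Day 7 + 12 = 19 and Day 8 + 16 = 24. A death between that visit and Day 28 has no later scheduled clinical-outcome rating. The documents give no rate for intolerance stops.

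7. **Section 7.5 against 8.1.** Section 7.5 exempts findings from the assessment of presenting signs and symptoms. Section 8.1 requires a report when baseline signs change in severity. A worsened presenting sign falls under both. Table 3 includes systolic pressure below 90 mmHg for bacteremia, a Part A indication. For cUTI/AP it includes nausea and vomiting, and Section 1.4 says "the less common TEAEs in patients were nausea, diarrhea, and vomiting". cUTI/AP patients enter only single-arm Part B, so that example bears on the description of ETX2514SUL safety and not on the comparison with colistin.

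**The case against.** The best defence is that clinical failure is a rating chosen at set visits and not an event. The 8.1 sentence comes straight after the one on newly emergent infections, so the natural contrast is between a new infection, which is an adverse event, and non-response of the index infection, which is an efficacy outcome. On that reading the underlying death or intolerance is still reported, as 8.1.1, 8.2, 8.5 and the planned tables assume. This is probably the intent, and many sites may act on it. But the text does not say so, and the defined term includes a toxicity event, so the intent has to be guessed.

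The defence does defeat several stronger inferences. A reader might conclude that deaths and intolerance stops are excluded from AE/SAE reporting. The protocol as a whole does not exclude them; it gives conflicting instructions. A reader might take 38.5% as the share of the primary population whose reports are at risk. It is simply the assumed death rate, and step 6 shows that some deaths are never rated as failures. A reader might also suppose that TEAEs leading to discontinuation are where the arms are most likely to differ. The documents do not say this, and the plan's primary safety comparison is RIFLE nephrotoxicity, which does not depend on adverse event filing.

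**Conclusion.** The contradiction holds. Protocol 8.1, read with 7.6 and SAP 5.5.1, conflicts with 8.1.1, 8.2, 8.3, 8.5, 9.2.4, 9.3 and SAP 9.4.1 on whether deaths and intolerance stops are reported. The consequence is possible inconsistency in SAE reports and in the tables of fatal SAEs and TEAEs leading to discontinuation. The primary endpoint, the RIFLE comparison and DSMB review of deaths have their own routes.

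The size cannot be estimated. About 46 deaths in 120 is the whole pool of assumed deaths in the primary population, resting on the protocol's mortality rates and equal arms. It measures neither lost reports nor the number of failures rated for death. The overlap between 7.5 and 8.1 is a smaller instance of the same problem. The matter deserves correction because it touches expedited reporting and the repair is short.

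**What to change.** Replace the 8.1 sentence with wording such as: *Lack of response, or progression, of the ABC infection under study is not by itself an adverse event. Any death, any event meeting a seriousness criterion, and any intolerance that leads to stopping study drug is reported as an AE or SAE even when the patient is also rated a clinical failure.*

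Reconcile 7.5 with the 8.1 text on baseline conditions by attribution: signs and symptoms attributable to the presenting infection are exempt, and those attributable to study drug or another cause, or meeting a seriousness criterion, are reported. Put the same qualifier in both sections. A rule that made every worsened presenting sign reportable would clash with the exemption for progression and leave sites with opposed instructions again.

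The definition of clinical failure in 7.6 and SAP 5.5.1 can stay as it is. The cost is a short amendment or site memo, some additional AE and SAE forms, and a query to sites on failures already rated for death or intolerance. No endpoint, sample size, treatment rule or analysis population changes.
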